**UNIVERSIDADE FEDERAL DE SANTA CATARINA
CAMPUS ARARANGUÁ-ARA**

[name]
[contact] / [name]

RESEARCH PROJECT

Dry Needling and Photobiomodulation in the treatment of Myofascial Pain

Study Principal Investigator: [name] [name].

ABSTRACT

Myofascial Pain is a clinical condition of myalgic pain characterized mainly by the presence of Myofascial Trigger Points. Trigger points can be active or latent and they are described as a hypersensitive spot within a taut band in the muscle. The use of a computer for long periods has been shown as a trigger the trigger points. Dry Needling and Low-Level Laser Therapy (LLLT) has been described as good resources to treat myofascial pain. The hypothesis is that the association of the purposed interventions will have greater effects than only the dry needling intervention. The objective is to evaluate the effects of the dry needling and the laser in the treatment of upper trapezius trigger point on women. This study is composed of an evaluation and an intervention proposal with dry needling and LLLT to treat myofascial trigger points. The sample will be composed of 60 women, with 18 to 65 years old, divided into three groups. Twenty individuals will be in group Dry-On that will receive dry needling intervention on the trigger point, followed by LLLT intervention on. Twenty individuals will be in group Dry-Off that will receive dry needling intervention on the trigger point, followed by LLLT intervention turned off. Twenty individuals will be in group Control that will receive dry needling intervention at 1.5 cm from the trigger point, followed by LLLT intervention turned off. All interventions will be performed in one session. Outcome measures for pain, pressure pain threshold, functionality, and muscle activity will be collected.

Key-words: Myofascial pain; Pressure Pain Threshold; Low-Level Laser Therapy; Dry needling;

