These effects can be explained on the red light spectrum, near to infrared (660nm-905nm), have good effects to reduce inflammation, relieve pain, and accelerate the tissue regeneration (22). According to Gerwin (4), 2010, the LLLT has level B of the recommendation of probable effect on the treatment of pain caused by myofascial trigger points. Gattie et al (23), 2017, in their systematic review, state that the current information on dry needling intervention, whether compared to placebo treatment or when compared to another intervention, has very low to moderate quality of evidence. Furthermore, although the trigger points demonstrate changes in muscle activation obtained through electromyography (EMG), there are few studies that present EMG findings in order to demonstrate the effects of dry needling directly on muscle activity (24,25)

In this context, the present study aims to answer if the association of dry needling and photobiomodulation will have a greater effect on the treatment of myofascial trigger points than the dry needling alone or the placebo treatment.

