2.2. Specific Objectives

To evaluate the pain level before, during, and after the dry needling and photobiomodulation applications on the trigger point.

To identify the pain pressure threshold before and after dry needling and photobiomodulation applications on the trigger point

To verify the electromyographic activity of upper trapezius before and after the proposed treatments

To compare the effects fond intra and inter-groups for the applications of dry needling, dry needling and photobiomodulation, and control protocol.

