3.6. Statistical Analysis

Data analysis will be performed through the GraphPad Prism[®] software, version 6.01 (GraphPad Software, La Jolla, California, USA). The Shapiro-Wilk test will be run to verify sample normality distribution. The Two-Way ANOVA test will be used for comparative analysis inter and intra-groups. The P value ($p < 0.05$) will be used to establish the significance of the results, in addition to the 95% Confidence Interval (95% CI). The values will be described as a mean \pm standard deviation.

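### Section 3.6 applies p < 0.05 to every between- and within-group ANOVA result without naming a deciding outcome, time, term or multiplicity rule, so no single 5% test answers the On-versus-Off hypothesis

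*Combined protocol and SAP*

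**What the plan says.** The Abstract gives the hypothesis: "The hypothesis is that the association of the purposed interventions will have greater effects than only the dry needling intervention". The Introduction widens the question by asking whether the combination "will have a greater effect on the treatment of myofascial trigger points than the dry needling alone or the placebo treatment". Neither attaches an outcome or a time.

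The Abstract lists the outcomes without ranking them: "Outcome measures for pain, pressure pain threshold, functionality, and muscle activity will be collected". Section 2.2 ranks none either, and it asks for comparisons of both kinds: "To compare the effects fond intra and inter-groups for the applications of dry needling, dry needling and photobiomodulation, and control protocol".

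Section 3.4 gives the schedule:
- VAS at baseline and four later times (T1 to T4).
- PPT at baseline and two later times.
- NDI at baseline, one week and one month.
- Two EMG variables, RMS and FMed. Their timing comes only from Section 2.2: "To verify the electromyographic activity of upper trapezius before and after the proposed treatments".

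On the analysis, Section 3.6 says: "The Two-Way ANOVA test will be used for comparative analysis inter and intra-groups". It then adds: "The P value ($p < 0.05$) will be used to establish the significance of the results, in addition to the 95% Confidence Interval". The rest of that section is the software, a normality test and the descriptive format. It does not name the ANOVA factors, the term that decides, any post-hoc test, any multiplicity adjustment, or the quantity to which the confidence interval belongs.

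**The concern.** A hypothesis test holds its 5% error rate only if the deciding result is known in advance. Here the analyst must still choose the outcome, the time, the ANOVA term (group, time or interaction), the post-hoc comparison, and whether a within-group or a between-group result counts. Some of these choices keep the false-positive rate near or below 5%, and others take it well above. The plan commits to none of them. A laser effect could therefore be reported on whichever result crosses 0.05, and a reader could not tell which p-value was meant to answer the hypothesis.

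The within-group comparisons raise a separate problem. A p-value for change in On and another for change in Off do not, even together, test whether On differs from Off.

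**Working it through.** **Inputs from the documents.** Three groups of 20 (Section 3.3), alpha 0.05 (Section 3.6), and the schedule in Sections 2.2 and 3.4. The plan gives no error rate, power or detectable difference to reproduce.

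**Assumptions.** Tests are two-sided (the plan does not say). EMG is read once after treatment. The documents give no correlations, so four settings are used (within a measure / across measures): 0/0, 0.5/0.2, 0.8/0.4 and 0.9/0.6.

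**1. Number of readouts.** VAS 4 + PPT 2 + NDI 2 + RMS 1 + FMed 1 = 10. The count is not firm. Treating EMG as one variable gives 9. Section 2.2 also mentions a pain reading during treatment that Section 3.4 does not schedule, and including it gives 11.

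**2. On versus Off, each readout tested at 0.05, no true effect.** If the readouts were independent: 1 - 0.95^10 = 40.1%. Simulation (20,000 trials per setting, t-tests, 20 per arm):

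| Correlation within / across | At least one p < 0.05 |
|---|---|
| 0 / 0 | 40.4% |
| 0.5 / 0.2 | 35.3% |
| 0.8 / 0.4 | 28.6% |
| 0.9 / 0.6 | 22.0% |

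The range is 19-37% for 9 readouts and 23-43% for 11.

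**3. Only results that wrongly favour On.** Each test then has a 2.5% chance. Under independence, 1 - 0.975^10 = 22.4%; over the four settings the rate is about 11-23%. This assumes a favourable direction for every readout. The documents give none for EMG; if RMS and FMed count in either direction, the range is 15-27%.

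**4. All three pairs of groups.** 3 x 10 = 30 comparisons, giving about 45-73% over the same settings.

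**5. Any of five group-by-time interactions.** Under independence, 1 - 0.95^5 = 22.6%. The four settings also give 22-23%. This event is a difference among any of the three groups, not On versus Off specifically.

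**6. Comparator.** One pre-named On-versus-Off test: 5% (4.8-5.1% in simulation).

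**7. Within-group p-values.** Suppose On and Off truly improve by the same amount, in SDs of change. Let p be the power of a paired t-test with n = 20. The groups are independent, so the chance that On is significant and Off is not is p(1 - p).

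| True change | p | On only, p(1 - p) | Disagreement, 2p(1 - p) |
|---|---|---|---|
| 0.3 SD | 0.247 | 0.186 | 0.37 |
| 0.4 SD | 0.397 | 0.239 | 0.48 |
| 0.5 SD | 0.564 | 0.246 | 0.49 |
| 0.6 SD | 0.721 | 0.201 | 0.40 |

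This approximates the planned ANOVA, which would normally pool the error across groups. With pooled error (57 df, two times), disagreement over the same range is 37-48%.

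**8. Detectable difference, 20 per arm, 80% power.** Normal approximation at 0.05: (1.960 + 0.842) x sqrt(2/20) = 0.886 SD; the t-based value is 0.909. At 0.05/2 = 0.025 the t-based value is 1.009 SD.

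**The case against.** **ANOVA already limits the comparisons.** If post-hoc On-versus-Off tests at post-treatment times were run only after a significant interaction, the rate of at least one false On-versus-Off result would fall to 9.0%, 5.3%, 3.2% and 2.5% in the four settings. That is a fair point, and it means inflation is not certain. But the plan states no such gate, and an ANOVA on one variable does nothing about there being five.

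**The 22-40% overstates the harm.** A reader might take it as the chance of a false claim that the laser helps. It is not: the hypothesis is directional, and the two-sided count includes results favouring Off. The figure for that claim is about 11-23%. This objection stands.

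**Nobody has said that within-group results will decide.** This also stands. A reader might infer that the investigators intend to claim a laser effect from On being significant and Off not. The documents do not say so; Section 2.2 lists the two kinds of comparison together. The gap is that Section 3.6 does not rule it out.

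**VAS is implicitly primary.** Pain is the first specific objective and VAS is an entry criterion, so a reader might infer its rank. Order in a list is not a ranking. The entry VAS (Section 3.3.1) also covers a different region and a 30-day recall, unlike the outcome VAS in Section 3.4.

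**The trial is small and exploratory.** Section 3.3 does describe a convenience sample. But the Abstract states a directional hypothesis, and Section 3.6 uses the threshold to establish significance, which is how a confirmatory test is worded.

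**Conclusion.** The point holds, and the plan should be changed. That no deciding test is named follows from the text alone and needs no assumption.

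Its size depends on assumptions the documents cannot settle: two-sided tests, one EMG reading after treatment, every readout tested at 0.05, and correlations of 0-0.9 within and 0-0.6 across measures. On those terms the chance of at least one On-versus-Off p < 0.05 with no true effect is about 22-40% (about 11-23% falsely favouring On). It is about 45-73% over all three pairs, and about 23% for any of five independent interactions. One pre-named test gives 5%. These are different events and should not be read as one scale.

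The within-group figure of about 19-25% is a paired-t approximation for an assumed equal improvement of 0.3-0.6 SD.

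Two stronger readings are not supported: that the planned analysis necessarily inflates error, since gating could keep it low, and that On versus control must be secondary, since the Introduction sets it beside On versus Off. The data remain usable. What is missing is a commitment about how to read them.

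**What to change.** Add to Section 3.6:

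1. One confirmatory test: On minus Off on one outcome at one time (for example VAS at one of T1 to T4), chosen by the sponsor before the data are seen, two-sided at 0.05.
2. The status of On versus control, which is the sponsor's decision. If it is also confirmatory, use Holm over the two contrasts (first step 0.05/2 = 0.025). If not, call it secondary. Report all other comparisons as estimates with the planned 95% CI, adjusted for multiplicity only if any is to be called significant.
3. Within-group changes reported as mean change with 95% CI, with no conclusion about an intervention resting on within-group p-values.

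This needs no extra participants or visits. The cost is that fewer results can be called significant. With 20 per arm, 80% power requires a true difference of about 0.91 SD for the single test, or about 1.01 SD at the first Holm step if both contrasts are confirmatory. Results reported only as estimates with 95% CI need no adjustment.

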3.7. Ethical Aspects

The present study is grounded on the ethical principles, with base on the Resolution n° 466 of December 12th, 2012, of the National Health Council, which incorporates under the individual and collectivities optics, the four basic references of the bioethics: autonomy, non-maleficence, beneficence, and justice, among others, aiming to ensure the rights and duties which concern the scientific community, the research subjects, and the State.

